5.3. Unmasking of the Randomization Codes

The complete randomization code will be unmasked after all the data queries related to the efficacy and safety outcomes have been resolved and the corresponding data revisions have been completed in the database. The DSMB Chair will review a limited set of unblinded tables and listings through DSMB meetings. The analyses for the DSMB meeting will be performed by an independent clinical research organization

6. ANALYSIS POPULATIONS

The following subject populations will be used for analysis:

The Intent-to-Treat (ITT) population will include all subjects who were randomized regardless of whether treatment was received. Subjects will be analyzed according to the treatment to which they were randomized.

The Safety population will include all subjects who receive at least one dose of study drug medication and data will be analyzed according to the treatment actually received. The safety analyses will be performed on the Safety population.

The per-protocol (PP) population will include all subjects who received the correct dose of study drug medication, have the 9-month VAS assessment, and do not have any protocol violations or major deviations as determined by Medical Monitoring. The per-protocol population will be determined in a blinded review before database lock. Subjects will be analyzed according to the treatment to which they were randomized. Primary efficacy analyses will be performed on the PP population.

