1.3.2. AMPUTATION

Amputation is considered when revascularization is not feasible due to the location and extent of atherosclerosis, when a patient is unable to tolerate a procedure, or when a patient is unlikely to have a functional extremity despite restoration of distal flow (e.g. due to dementia, chronic illness, etc.). While amputation does eliminate the source of pain at rest and all necrotic tissue,¹¹ it is associated with a significantly elevated perioperative and one year mortality rate.^{1,6,16}

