10. EFFICACY ANALYSES

The primary efficacy analysis will be based on the PP analysis population. Additional efficacy analyses will be performed on the ITT population.

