10.1.2. Imputation Methods of VAS Results for the ITT Population

In order to include all subjects in the ITT population, the following imputation rules will be applied for analysis of the ITT population.

For subjects without the primary efficacy endpoint (VAS change from baseline to 9 months), the following imputation methods will be applied:

- For missing Baseline VAS, assign the VAS score at Screening if the VAS score at Day 0 is missing.
- For missing 9 month VAS, assign the 12 month VAS score if the 9 month VAS is missing.

- For missing 9 month VAS, assign the last reported VAS prior to the 9 month VAS visit if both the 9 month and 12 month VAS assessments are missing.

For subjects who had a major amputation or limb procedure carried out, the following imputation methods will be applied:

- For subjects with a major amputation, assign the post baseline VAS score prior to the amputation.
- For subjects with a limb salvage, assign the post baseline VAS score prior to the intervention.

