10.2.1.1 Imputation Methods of VAS Results for the ITT Population

For subjects without the efficacy endpoint (VAS change from baseline to any post baseline result), the following imputation methods will be applied:

- For missing Baseline VAS, assign the VAS score at Screening if the VAS score at Day 0 is missing.
- For any post baseline VAS, assign the post baseline VAS score prior to the missing post baseline VAS via the last observation carried forward (LOCF) method.

For subjects who had a major amputation or limb procedure carried out, the following imputation methods will be applied:

- For subjects with a major amputation, assign the VAS score prior to the amputation.
- For subjects with a limb salvage, assign the VAS score prior to the intervention.

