Safety Population

Intervention	Placebo (N=)	VM202- 8 mg (N=)	VM202- 16 mg (N=)
PTA	n (%)	n (%)	n (%)
Peripheral bypass	n (%)	n (%)	n (%)
Amputation above the knee	n (%)	n (%)	n (%)
Amputation below the knee	n (%)	n (%)	n (%)
Atherectomy	n (%)	n (%)	n (%)
Surgical bypass	n (%)	n (%)	n (%)
Endarterectomy	n (%)	n (%)	n (%)
Thrombectomy	n (%)	n (%)	n (%)
Stent placement	n (%)	n (%)	n (%)
Other	n (%)	n (%)	n (%)

path\t_program.sas date time

Table 5.1.1
Visual Analogue Scale for Pain (mm)
Per-Protocol Population

	----- Placebo (N=) -----		--- VM202- 8 mg (N=) ---		--- VM202- 16 mg (N=) --	
	Result	Change ^[2]	Result	Change ^[2]	Result	Change ^[2]
Baseline ^[1]						
N		n		n		n
Mean (SD)		xx.x (xx.xx)		xx.x (xx.xx)		xx.x (xx.xx)
Median		xx.x		xx.x		xx.x
Min, Max		xx, xx		xx, xx		xx, xx
Day 14						
N		n		n		n
Mean (SD)		xx.x (xx.xx)		xx.x (xx.xx)		xx.x (xx.xx)
Median		xx.x		xx.x		xx.x
Min, Max		xx, xx		xx, xx		xx, xx
Comparison vs. Placebo						
Model 1 ^[3]						
LS Means (SE)			xx.x (xx.x)		xx.x (xx.x)	
LS Mean Differences (SE)				xx.x (xx)		xx.x (xx)
95% CI for LS Mean Differences				(xx.x, x.xx)		(xx.x, x.xx)
Overall p -value for Treatment Differences						x.XXXX
Pairwise p -value vs. Placebo (Dunnett's test)				x.XXXX		x.XXXX
Baseline vs. Day 14 (Paired t-test)			x.XXXX	x.XXXX		x.XXXX
Model 2 ^[4]						
Overall p -value for Treatment Differences (Jonckherre-Terpstra test)						x.XXXX
Pairwise p -value vs. Placebo (Wilcoxon Rank Sum test)				x.XXXX		x.XXXX
Baseline vs. Day 14 (Wilcoxon Signed Rank test)			x.XXXX	x.XXXX		x.XXXX

^[1] Baseline defined as the last non-missing value prior to first dose of study drug.

^[2] Change = Change from Baseline

^[3] One-way analysis of variance (ANOVA) with treatment groups as a factor.

^[4] Nonparametric tests for differences across a one-way classification of treatment.

path\t_program.sas date time

Programmer Note Repeat for all available time points, Day14, Day 28, Day 42, Day 90, 6mo, 9mo, and 12mo.

Programmer Note Tables 5.1.2 will be identical to Table 5.1.1 for the ITT Population using imputation rules specified in Section 10.1.2 of the Statistical Analysis Plan.

Table 5.2.1
Visual Analogue Scale for Pain- Percent (%) Change from Baseline
Per-Protocol Population

	Placebo (N=) Change ^[2]	VM202- 8 mg (N=) Change ^[2]	VM202- 16 mg (N=) Change ^[2]
Day 14- Percent (%) Change from Baseline ^[1]			
N	n	n	n
Mean (SD)	xx.x (xx.xx)	xx.x (xx.xx)	xx.x (xx.xx)
Median	xx.x	xx.x	xx.x

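### The per-protocol primary pain analysis can count relief after amputation or limb salvage as improvement, because the SAP's pre-procedure VAS rule covers ITT only

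*SAP*

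**What the plan says.** SAP section 6 defines the per-protocol (PP) set as patients who received the correct dose, "have the 9-month VAS assessment, and do not have any protocol violations or major deviations as determined by Medical Monitoring". Membership is settled in a blinded review before database lock. The same section then says: "Primary efficacy analyses will be performed on the PP population". Section 10 repeats the choice of population: "The primary efficacy analysis will be based on the PP analysis population". ITT analyses are additional. Protocol 6.2.1 has the same order, with its efficacy dataset primary and ITT secondary, and it undertakes to explore any inconsistency between the two.

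SAP 10.1 defines the endpoint as 9-month VAS minus baseline VAS, with no exception for a limb procedure in between. The exception appears in 10.1.2, which is headed for ITT and opens: "In order to include all subjects in the ITT population, the following imputation rules will be applied for analysis of the ITT population". It then says: "For subjects with a major amputation, assign the post baseline VAS score prior to the amputation". A parallel line covers limb salvage. Section 10.2.1.1, also headed for ITT, words the rule differently: "For subjects with a major amputation, assign the VAS score prior to the amputation". The Appendix B programmer note reads: "Tables 5.1.2 will be identical to Table 5.1.1 for the ITT Population using imputation rules specified in Section 10.1.2". Table 5.1.1, the PP table, carries no such instruction.

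Protocol 1.3.2 states why this matters for a pain score: "While amputation does eliminate the source of pain at rest and all necrotic tissue".

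**The concern.** The SAP recognises that a VAS taken after an amputation or limb salvage does not measure response to the drug, and it has a rule for that. The rule governs the secondary analysis and not the primary one. Nothing in the documents makes such a procedure a PP exclusion. Tables 11.1.1 and 11.2.1 plan to report amputation and limb salvage within PP, so such patients are expected there.

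The 9-month VAS requirement is a second, separate selection. Patients who die or withdraw before that assessment leave the primary analysis because of something that happened after randomisation.

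SAP section 4 says the trial was sized to estimate effect sizes and variability for a pivotal study. If arms differ in procedure rates, the headline pain difference mixes drug effect with surgery, and that figure is the one carried forward.

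**Working it through.** **Inputs from SAP section 4.** Mean improvement 30 (high dose), 28 (low dose) and 10 (placebo); SD 25; 20:20:10 patients; overall F-test at 5%. Improvement is taken as positive. Planned differences from placebo are 20 and 18 mm, average 19 mm (average active mean 29).

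**The plan's own power figure.**
- Weighted mean = (20×30 + 20×28 + 10×10)/50 = 25.2.
- Noncentrality = (20×4.8² + 20×2.8² + 10×15.2²)/25² = 2928/625 = 4.685.
- With 2 and 47 degrees of freedom, power is 45.1%, against the stated 49%. That gap is a separate matter; 45% is the reference below.

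**Assumptions not in the documents.** Improvement after amputation is 50 mm (range 40 to 60), with SD 25 also after amputation. Amputation rates are 10% or 20% per arm. Unless stated, all amputees attend month 9 and stay in PP, and group sizes stay at 20:20:10. Rejection rates come from simulating the F-test.

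Arm mean = (1 − q) × planned mean + q × post-amputation improvement, where q is the arm's share of amputees.

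**Case A: 20% placebo, 10% active, planned drug effect.**
- High: 0.9×30 + 0.1×50 = 32.0. Low: 0.9×28 + 0.1×50 = 30.2. Placebo: 0.8×10 + 0.2×50 = 18.0.
- Differences are 14.0 and 12.2 mm, average **13.1 mm**; power about 23%.
- At 40 mm: 30.1 − 16.0 = 14.1 mm. At 60 mm: 32.1 − 20.0 = 12.1 mm.
- If half the amputees leave PP (about 10% and 5% remaining): active 0.95×29 + 0.05×50 = 30.05, placebo 0.9×10 + 0.1×50 = 14.0, difference about **16 mm**; power about 32%.

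**Case B: no drug effect (all means 10), 20% active, 10% placebo.**
- Active: 0.8×10 + 0.2×50 = 18.0. Placebo: 0.9×10 + 0.1×50 = 14.0.
- Spurious benefit **4 mm**; F-test rejection about 5.6%.

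**Case C: 10% in every arm, planned drug effect.**
- If relief replaces the drug response: 0.9×19 = 17.1 mm. If it adds to it: 19 mm.

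**With the pre-procedure rule applied to PP.**
- Case A, zero change before amputation: 0.9×29 − 0.8×10 = 26.1 − 8.0 = **18.1 mm**; power about 38%.
- Case A, 10 mm worsening before amputation: (26.1 − 1.0) − (8.0 − 2.0) = 25.1 − 6.0 = **19.1 mm**.
- Case B, zero change: 8 − 9 = −1 mm.
- Case C, zero change: 17.1 mm, the same as when relief replaces the drug response, so the rule does not alter that figure.

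**The case against.** The strongest reply is that the plan already contains the check. ITT is pre-specified with the rule, protocol 6.2.1 commits to exploring disagreement, PP is fixed blind, and safety is the primary objective in SAP 2.1. This stands as mitigation. It does not correct the primary estimate, and the blinded review has no written criterion for procedures.

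The size also rests on stacked assumptions. Some amputees would leave PP through incorrect dosing, a Medical Monitoring decision or discontinuation; SAP Table 1 lists intervention for acute limb ischemia as a discontinuation reason. Entry sets no minimum VAS and allows ulcer or gangrene without rest pain, so a 50 mm gain is not available to everyone. The 5.9 mm shift in Case A (19 − 13.1) is below one standard error of the pooled contrast, 25×√(1/40 + 1/10) = 8.8 mm. All of this stands, which is why the figures are illustrative.

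Nor is the pre-procedure rule neutral. Its answer depends on the pain course before the procedure, and choosing it over the observed score is partly a choice of estimand. That supports reporting both.

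A reader might infer that the rule should cover only the treated leg. The documents do not support this: protocol 4.2.7 asks for current pain intensity without naming a leg, so a procedure on the other leg can lower the score too.

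**Conclusion.** The concern holds: the primary estimate can include post-procedure relief, and the SAP's own safeguard does not reach it. Under the stated assumptions, a 10-point excess of amputations on placebo takes about 6 mm off a planned 19 mm difference, or about 3 mm if half the amputees leave PP. The reverse imbalance with no drug effect creates about 4 mm of apparent benefit. The direction is unknown in advance.

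Two stronger readings are tempting. One is that the plan materially inflates false positives; in Case B rejection stays at about 5–6%, so the harm is to the estimate. The other is that procedures bias the result whatever their distribution. With equal rates the difference shrinks only if relief replaces the drug response, and the rule does not restore it.

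That the rule is missing from PP is plain from the text; the size is uncertain because the documents give no event rates for this trial. The effect of excluding deaths and withdrawals through the 9-month VAS requirement is not quantified. This should be fixed before unblinding.

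**What to change.** 1. In SAP sections 6 and 10, make ITT (all randomised, by randomised arm, with the 10.1.2 rule) the primary efficacy analysis and PP supportive. Align protocol 6.2.1.
2. If PP is kept as primary, apply the 10.1.2 pre-procedure rule to it and to its table programs (5.1.1, 5.2.1, the PP tables in the 5.3 series, and 5.4.1).
3. Do not restrict the rule to the treated leg.
4. Use the same wording in 10.1.2 and 10.2.1.1, and assign baseline VAS (zero change) when no post-baseline VAS precedes the procedure.
5. Report the analysis of observed 9-month VAS as a sensitivity analysis, because the rule is itself an assumption.

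The cost is SAP wording, some table programming and a small amendment to protocol 6.2.1, which may need IRB approval under protocol section 13. No new data are needed. The downside is a possibly more conservative estimate, and ITT still relies on carried-forward scores for deaths and dropouts.

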7. SUBJECT DISPOSITION

Subject disposition information will be summarized for all subjects by dose cohort. Summaries will include the number of subjects:

- enrolled (overall)
- in each analysis population
- who received all planned doses of VM202
- last visit attended (Note: subject considered to have attended a visit if at least one assessment was reported for that visit)
- who completed the study (as determined by Study Exit Status page)
- primary reason for discontinuation for those who did not complete the study

8. DEMOGRAPHIC AND BASELINE CHARACTERISTICS

Demographic and baseline characteristics will be summarized for the ITT, Safety and PP analysis populations. Demographic variables include:

- age at informed consent
- sex
- race

Baseline variables will include height, weight, and incidence of diabetes mellitus and renal dysfunction. Age, height and weight will be compared among treatment groups (overall

comparison) using the method for continuous variables. All other variables will be compared among groups (overall comparison) using the method for categorical variables.

9. MEDICAL HISTORY

Medical history will be categorized by body system. Medical history and peripheral vascular disease intervention history at baseline will be summarized by frequencies and rates on the Safety population.

10. EFFICACY ANALYSES

The primary efficacy analysis will be based on the PP analysis population. Additional efficacy analyses will be performed on the ITT population.

10.1. Primary Efficacy Variable

Subjects will be asked to assess the level of pain they feel by placing a perpendicular line on a scale of 0 (No Pain) to 100 (Pain as bad as it can be) at each visit. The subject's Visual Analogue Scale (VAS) score will be determined by where the subject places the perpendicular line by two independent readers. The average scores from the two readers will be used as the pain score for the corresponding subject. If a score is reported by only one reader, then that score will be assigned as the pain score. The primary efficacy endpoint is the change in pain level between baseline and the 9-month follow-up as determined by VAS. The change in pain will be calculated for each subject as follows:

$$\text{Change} = 9\text{-month VAS} - \text{Baseline VAS}$$

Since higher VAS indicates worse pain, a negative value of change means an improvement, and a positive value of change means deterioration.

The mean change in pain will be compared among the three treatment groups. The statistical null and alternative hypotheses for the primary efficacy endpoint are:

$$\begin{aligned} H_0: \mu_H &= \mu_L = \mu_P \text{ and} \\ H_a: \text{at least one of the three } \mu's &\text{ is different,} \end{aligned}$$

where μ_H , μ_L , and μ_P are mean change in pain from baseline to 9-month follow-up for VM202 high dose, VM202 low dose, and placebo groups, respectively.

One-way Analysis of Variance (ANOVA) with treatment (VM202 high dose, VM202 low dose, and placebo) as the factor will be used to compare the mean change in pain among the three treatment groups. Dunnett's test will be used to compare the mean change in pain level between VM202 high dose to placebo and between VM202 low dose to placebo. This analysis will be repeated using Percent (%) Change from Baseline, where Percent Change from Baseline is defined as:

- % Change from Baseline = [(9 month VAS – Baseline VAS)/Baseline VAS]* 100

An additional set of analyses will be run using non-parametric tests as described in Section 5.2 for continuous variables.

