4.2.7. VISUAL ANALOG SCALE (VAS) SCORE

Pain will be measured using the visual analog scale (VAS) at screening, before the first treatment (injection) on Day 0, pretreatment on Days 14, 28 and 42, Day 90, 6 months, 9 months and 12 months. The VAS scoring instrument is a 10-cm line, oriented horizontally, with the left end indicating “no pain” and the right end representing “pain as bad as it can be”. The patient is asked to mark a place on the line corresponding to the current pain intensity. The distance along the scale is then converted into a numeric reading as detailed in the study manual.

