Appendix 1. Schedule of Evaluations and Visits

SCHEDULE OF EVALUATIONS AND VISITS

PROCEDURE	Screening / Baseline (-60 – 0 D)	1 st Injection Day 0		2 nd Injection Day 14 ± 3 D		3 rd Injection Day 28 ± 3 D		4 th Injection Day 42 ± 3 D		Day 49 ± 3 D	Day 90 ± 7 D	6 mo ± 1 mo	9 mo ± 1 mo	12 mo ± 1 mo	Early Withdrawal
		Pre- dose	Post- dose	Pre- dose	Post- dose	Pre- dose	Post- dose	Pre- dose	Post- dose						
Baseline Evaluation															
Informed Consent	✓														
Complete Medical History	✓														
Complete Physical Exam	✓														
Cancer screening [†]	✓														
Viral screening – HIV, HTLV, HBV, HCV	✓														
Urinalysis	✓														
ECG	✓														
Pregnancy test	✓														
Safety and Efficacy Parameters															
Retinal Fundoscopy	✓													✓	✓
Vital Signs	✓	✓	✓	✓	✓	✓	✓	✓	✓	✓	✓	✓	✓	✓	✓
Concomitant Medications	✓	✓		✓		✓		✓		✓	✓	✓	✓	✓	✓
Serum Chemistry and hematology	✓	✓		✓		✓		✓		✓	✓	✓	✓	✓	✓
Copies of VM202 in whole blood		✓	✓**					✓	✓**	✓	✓	✓			✓ ¹
Serum HGF		✓						✓		✓	✓				✓ ¹
Visual Analog Scale (VAS) score	✓	✓		✓		✓		✓			✓	✓	✓	✓	
VascuQol		✓									✓		✓	✓	
ABI & TBI	✓	✓				✓					✓	✓	✓	✓	
TePO ₂	✓	✓										✓	✓	✓	
Photograph and measurement of ulcer(s) ^{††}	✓	✓		✓		✓		✓		✓	✓	✓	✓	✓	✓
Rutherford Classification	✓											✓	✓	✓	
MRA (at designated site(s) only) ^{†††}		✓										✓	✓		
Treatment															
Injection site reaction assessment			✓	✓	✓	✓	✓	✓	✓	✓					✓ ²
Adverse Events			✓	✓	✓	✓	✓	✓	✓	✓	✓	✓	✓	✓	✓

† Includes: cancer markers (carcinoembryonic antigen (CEA), alpha fetoprotein (AFP), CA19-9, and CA125 (females only)); chest X-ray or CT scan of the chest (if patient has a previous history of tobacco use, a CT scan will be performed instead of the chest X-ray) within 3 months; pap smear and mammogram if not performed within past 12 months (females only); PSA (males only); for patients ≥ 50 years old, colonoscopy within past 10 years

†† If present prior to first study drug administration

††† 7 days prior to Day 0; ±7 days to Month 6 and Month 9

** 2 hours after injection (± 1 hour)

1 If withdrawal occurred before Day 90 Visit

2 If withdrawal occurred before Day 49 Visit

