4. SAMPLE SIZE JUSTIFICATION

The sample size for this Phase 2 study was chosen to estimate effect sizes and variability for a pivotal study. Assuming a standard deviation for change in VAS scores of 25, a mean change of 30 in the high dose group, 28 in the low dose group, and 10 in the placebo group, an Analysis of Variance (ANOVA) F-test at alpha of 5%, a sample size of 20:20:10 for high dose, low dose and placebo, respectively, will have 49% power to detect an overall difference among treatment groups.

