5.2. Statistical Methods

Two-sided p -values < 0.05 will be considered statistically significant, unless otherwise stated.

Separate statistical tests will be performed at each time point for key endpoints of interest.

In general, an overall test to determine if there is a statistically significant difference among the three treatment arms will be conducted first. Further comparisons will be made to determine if either the low or high dose groups are significantly different from the placebo group.

For continuous variables, a one-way analysis of variance (ANOVA) with treatment group (high dose, low dose, and placebo) as a factor will be used to determine if there is a significant difference among the groups. The low and high dose groups will each be compared against the placebo group using Dunnett's test. The mean difference between the VM202 groups versus placebo along with 95% confidence intervals for the mean difference will also be presented. To be viewed as secondary, an additional set of analyses will be run using non-parametric tests. A Jonckheere-Tepstra test will be applied to the VAS change from baseline results to detect overall trend differences. Non-parametric pairwise treatment comparisons versus placebo will also be made using Wilcoxon Rank Sum test. Within each treatment group for each endpoint, both a paired t-test (parametric) and Wilcoxon Signed Rank test will be run to test for differences comparing baseline to each post-baseline assessment.

For categorical variables, Fisher's exact test will be used to determine if there is a significant difference among the three treatment groups. Separate Fisher's exact tests will be used to compare the low and high dose groups to the placebo group.

For time-to-event variables (such as amputation, limb salvage and mortality), Kaplan-Meier estimates will be used to estimate survival times. Differences in survival times will be compared among groups using the log-rank test.

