10.1.1. Subgroup Analysis

It is clinically considered that sex and co-morbidities (diabetes or renal dysfunction) can affect the change in pain. A two-factor ANOVA with treatment and one of the covariates (sex, diabetes, or renal dysfunction) as the factors will be used to analyze the primary endpoint. For each analysis, treatment group, covariate, and treatment group by covariate interaction will be included in the model. If the treatment by covariate interaction is judged to be insignificant ($p > 0.10$) then the interaction term will be removed from the model and pairwise treatment comparisons of adjusted means vs. Placebo using Dunnett's test will be presented. If the treatment by covariate interaction term is significant, then separate analyses will be performed for the different levels of the covariate of consideration.

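### The primary VAS analysis leaves out baseline VAS as a covariate, giving up precision that would cost one error degree of freedom

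*SAP*

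**What the plan says.** SAP 10.1 defines the primary efficacy endpoint as 9-month VAS minus baseline VAS and names the model: "One-way Analysis of Variance (ANOVA) with treatment (VM202 high dose, VM202 low dose, and placebo) as the factor will be used". Dunnett's test then compares each dose with placebo.

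The same model appears elsewhere in the SAP:

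- **Section 5.2, general method:** "For continuous variables, a one-way analysis of variance (ANOVA) with treatment group (high dose, low dose, and placebo) as a factor will be used".
- **Table 5.1.1 shell, model footnote:** "One-way analysis of variance (ANOVA) with treatment groups as a factor".
- **Section 10.2.1:** VAS at the other visits follows the methods of 10.1.

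The only other parametric VAS models are in 10.1.1: "A two-factor ANOVA with treatment and one of the covariates (sex, diabetes, or renal dysfunction) as the factors will be used". Baseline VAS is not among those covariates. The percent-change repeat uses baseline as a denominator, and the rank tests and the CMH test carry no baseline term.

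The measurement is planned for everyone. Protocol 4.2.7 states: "Pain will be measured using the visual analog scale (VAS) at screening, before the first treatment (injection) on Day 0". The row "Visual Analog Scale (VAS) score" in Protocol Appendix 1 is ticked at both of those points.

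On purpose and variability, SAP Section 4 says that the sample size "was chosen to estimate effect sizes and variability for a pivotal study", and gives one spread: "Assuming a standard deviation for change in VAS scores of 25". Protocol 6.2.1 names no model for the primary comparison.

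**The concern.** A change-score ANOVA uses baseline with its slope fixed at 1. ANCOVA estimates the slope from the data. When the true slope is not 1, the change score leaves baseline-related variation in the error term.

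Two features make this relevant here. Protocol 3.3.1 admits patients with ulcers or focal gangrene without requiring rest pain, and it sets no minimum VAS. Baseline pain may therefore vary widely, and patients near 0 have no room to improve. Also, the placebo arm has only 10 patients and no stratification is described, so a chance difference in baseline pain is quite possible. Table 5.1.1 would show such a difference by arm, but showing it does not adjust for it.

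At stake is the precision of the dose-placebo differences, which is what a trial sized to inform a pivotal study most needs to deliver. Bias is not at stake.

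**Working it through.** **Inputs from SAP Section 4:** SD of change 25; mean changes 30 (high dose), 28 (low dose) and 10 (placebo); 20:20:10; F-test at 5%; stated power 49%.

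**Assumed, because the documents do not give them:** correlation r between baseline and 9-month VAS of 0.3, 0.5 or 0.7; ratio k = 9-month SD / baseline SD of 0.8, 1, 1.25 or 1.5; a common slope in all arms.

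**Step 1: the SAP's own figure.**
- Weighted grand mean = (20×30 + 20×28 + 10×10)/50 = 25.2.
- Sum of squares = 20×4.8² + 20×2.8² + 10×15.2² = 2928.
- Noncentrality = 2928/625 = 4.685. With 2 and 47 df, power is 45.1%, not 49%.
- Using the unweighted grand mean (22.67) gives noncentrality 5.198 and 49.3%, which is close to the stated figure but is not the correct noncentrality for unequal groups. That is a separate matter; 45.1% is the comparator below.

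**Step 2: cost of the extra term alone.** Error df fall from 47 to 46. If baseline is unrelated to change, and chance imbalance is ignored, power goes from 45.11% to 45.05%.

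**Step 3: ANCOVA under the assumed range.** Let sb be the baseline SD.
- Variance of change: sb²(1 + k² − 2rk) = 625, which fixes sb.
- Residual variance: k²sb²(1 − r²).
- Average cost of chance baseline imbalance: divide the noncentrality by 1 + 1/45.
- SE of an active-placebo contrast (20 v 10): residual SD × √0.15 × √(1 + 1/45). Unadjusted: 25 × √0.15 = 9.68 mm.
- Shift in the change-score contrast from a 1-SE baseline difference: (1 − rk) × sb × √0.15.

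Example, k = 1 and r = 0.5: sb = 25; residual variance = 625 × 0.75 = 468.75 (SD 21.65); noncentrality = 2928/468.75/(1 + 1/45) = 6.11; power 56.3%; SE 8.48 mm; shift 0.5 × 25 × 0.387 = 4.84 mm.

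Each cell gives r = 0.3 / 0.5 / 0.7:

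| k | Power, % (ANOVA 45.1) | Contrast SE, mm (ANOVA 9.68) | 1-SE shift, mm |
|---|---|---|---|
| 0.8 | 74.8 / 68.8 / 64.4 | 6.94 / 7.40 / 7.76 | 6.83 / 6.34 / 5.91 |
| 1 | 62.8 / 56.3 / 50.8 | 7.89 / 8.48 / 9.03 | 5.73 / 4.84 / 3.75 |
| 1.25 | 54.3 / 48.7 / 45.0 | 8.67 / 9.25 / 9.69 | 4.49 / 3.17 / 1.34 |
| 1.5 | 49.7 / 45.6 / 44.3 | 9.14 / 9.61 / 9.78 | 3.47 / 1.83 / −0.45 |

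Simulation with random baselines (20,000 runs per cell) agrees with every power figure to within 1 percentage point. The planned differences from placebo are 18 and 20 mm.

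**Step 4: break-even.** With the imbalance allowance, ANCOVA gains once the absolute correlation of baseline with change exceeds about 0.15.

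**Step 5: smaller per-protocol set.** At an assumed 16:16:8, power goes from 36.5% to 63/57/53% (k = 0.8), 52/46/41% (k = 1), 44/39/36% (k = 1.25) or 40/37/36% (k = 1.5).

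**Step 6: slopes that differ between arms.** Assumed baseline SD 25 and residual SD 18, no treatment difference in mean change, 40,000 runs:

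| Slope, active / placebo | ANOVA type I error | ANCOVA type I error |
|---|---|---|
| 0.5 / 0.5 | 5.1% | 5.0% |
| 0.4 / 0.6 | 4.3% | 5.1% |
| 0.2 / 1.0 | 3.8% | 7.0% |
| 1.0 / 0.2 | 8.6% | 7.1% |

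Neither model is protected when slopes differ strongly.

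**The case against.** The best defence is that nothing here is wrong. The ANOVA is valid, the SAP's primary objective is safety, VAS change falls under a secondary objective, and the trial is not confirmatory. The gain rests wholly on assumed values. Two of the twelve cells show no gain (k = 1.25 and k = 1.5, both at r = 0.7), two more gain under 4 points (the same k at r = 0.5), and nothing in the documents favours k at or below 1. All of this stands, and it limits the point to a recommendation.

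It is also true that the 1-SE shift is not a second benefit. In each cell, the squared shift plus the ANCOVA contrast variance before the 1 + 1/45 factor equals 9.68². For k = 1 and r = 0.3, 5.73² + 7.80² = 9.68². The planned interval already allows for chance imbalance on average. The shift shows the same gain conditionally, for a trial in which the imbalance has occurred, and the two must not be added.

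With strongly unequal slopes ANCOVA can exceed 5%. So can the ANOVA, in the opposite pattern. That supports a slope check and a retained sensitivity analysis more than it supports leaving baseline out.

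Finally, no calculation here covers the 10.1.1 analyses split by covariate level, the other visits, or ITT data with carried-forward and pre-amputation scores.

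**Conclusion.** The point holds as an efficiency recommendation. No VAS model in the SAP adjusts for baseline VAS, although the change score already requires that value. Adjustment would be expected to narrow the dose-placebo differences and to correct for an observed baseline imbalance.

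The size of the gain is not determined by the documents. With a common slope and the change SD held at 25, power ranges from 75% down to 44% against 45% unadjusted, so the worst cell loses about 1 point. The gain is largest when the correlation is low and the 9-month SD does not exceed the baseline SD. Confidence is medium, because r, k and the common slope are all assumed.

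**What to change.** - **SAP 10.1:** make the primary model an ANCOVA of 9-month VAS (or change) on treatment with baseline VAS as covariate, with Dunnett comparisons of adjusted means against placebo. Adjusted means with Dunnett's test are already planned in 10.1.1. Word the hypotheses in terms of adjusted means.
- **SAP 10.1.1 and 10.2.1:** add the same term to the subgroup models and the by-visit analyses of VAS change.
- **Sensitivity:** keep the change-score ANOVA, and examine the treatment-by-baseline slope descriptively.
- **Shells:** update the model footnotes in Tables 5.1.x and 5.3.x.
- **Section 4:** note that the power statement refers to the unadjusted F-test.
- **Percent change:** this may stay as a secondary analysis, with a stated rule should any baseline be 0.

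The Section 5.2 method for other variables need not change. The cost is SAP wording, one model term and one error df (47 to 46 with 50 analysed). No new data are needed and no patient is lost, since SAP 10.1.2 already substitutes the screening VAS in the ITT set when Day 0 is missing. The change should be made before the randomisation code is released.
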